## 6.5 Toxicity

Toxicities will be graded and reported according to the NCI Common Toxicity Criteria for Adverse Events (CTCAE) Version 3.0 as linked in Appendix C. This document can also be downloaded from the Cancer Therapy Evaluation Program (CTEP) home page <<http://ctep.info.nih.gov>>.

Should a report of an infection (any grade) arise, please identify the bacteria or fungus related and report the event via Serious Adverse Event form. In particular, if any organisms are identified as anaerobic, infectious disease should be consulted for management using standard of care relevant to anaerobic bacterium.

## 6.6 Schedule of Assessments

The schedule of assessments for the trial is shown in Appendix B. If a required observation or procedure is missed, documentation is required on the Protocol Deviation Form, to explain the reason for this protocol deviation.

### Prestudy Assessments

The following evaluations will be performed within 4 weeks of the tumor debulking laparotomy (unless otherwise specified):

1. A signed Patient Informed Consent Form for tissue harvest must be obtained.
2. It has been confirmed that the patient meets all tissue procurement inclusion criteria and none of the exclusion criteria.
3. A complete medical history must be obtained.
4. A physical examination (including vital signs, height, and body weight) must be obtained.
5. Assessment of PS on the ECOG scale (see Appendix A) must be obtained.
6. Radiological assessment of tumors (i.e., chest X-ray, (chest CT or MRI only if indicated), pelvic/abdominal CT or MRI) used to stage the extent of disease must be performed within 6 weeks. The methods used for prestudy assessments (e.g., CT or MRI) should be used throughout the study. If possible, the same equipment should be used each time.

7. A complete blood count (CBC) with differential and platelet count must be performed. (HIV testing is not required if the subject has no medical history of HIV).
8. CA-125 tumor assessment (at initial diagnosis per medical history).
9. Routine pre-operative serum chemistries (including but not limited to creatinine, total bilirubin, alkaline phosphatase, and aspartate transaminase (AST) and/or alanine transaminase (ALT)).
10. Immune function analysis consisting of ELISPOT analysis of cytotoxic T cell reaction to autologous tumor antigens will be obtained at tissue harvest. (within 24 hours before tissue procurement or on the day of harvest)

Following tissue procurement, patients will be contacted every 6 weeks  $\pm$ 2 weeks to assess interest / eligibility of the main randomized portion of the trial and survival status. Blood for immune function analysis will be collected prior to the first and third cycles of ( $\leq$ 24 hours before) chemotherapy post debulking. Medical records should be provided to support continued eligibility.

The following evaluations will be performed on all subjects within 2 weeks of registration / randomization (unless otherwise specified):

1. A signed protocol specific Patient Informed Consent Form must be obtained.
2. It has been confirmed that the patient meets all inclusion criteria and none of the exclusion criteria.
3. An interval medical history must be obtained within 4 weeks.
4. A physical examination (including vital signs, oxygen saturation, height, temperature and body weight) must be obtained.
5. Assessment of concomitant medications
6. Assessment of PS on the ECOG scale (see Appendix A) must be obtained.
7. A tumor clinical assessment of the patient's disease (i.e., by physical examination) must be performed within 4 weeks.
8. Radiological assessment of disease status (i.e., chest X-ray, (chest CT or MRI only if indicated), pelvic/abdominal CT or MRI) used to stage the extent of disease must be performed within 4 weeks. The methods used for prestudy assessments (e.g., CT or MRI) should be used throughout the study. If possible, the same equipment should be used each time.
9. A complete blood count (CBC) with differential and platelet count must be performed. (HIV testing is not required if the subject has no medical history of HIV).
10. CA-125 tumor assessment within 4 weeks following completion of surgery chemotherapy. If the CA-125 is  $>20$  U/mL, the patient can continue with serial CA-125 evaluations up to 2 months if the levels

continue to decrease and there is no objective evidence of disease recurrence.

11. Serum chemistries (creatinine, glucose, total protein, blood urea nitrogen (BUN), total carbon dioxide (CO2), albumin, total bilirubin, alkaline phosphatase, and aspartate transaminase (AST) and/or alanine transaminase (ALT)) and electrolytes (total calcium, chloride, potassium, sodium) must be performed.
12. Immune function analysis consisting of ELISPOT analysis of cytotoxic T cell reaction to autologous tumor antigens.
13. Urinalysis must be performed.
14. EKG must be performed.
15. FACT-O, Version 4 assessment

### **Assessments During Treatment**

The following evaluations will be performed monthly (every 28 days  $\pm$ 3 days) during the therapy (unless otherwise specified):

1. A physical examination, including vital signs and body weight.
2. A toxicity assessment (adverse events).
3. Assessment of concomitant medications taken.
4. Tumor response by clinical assessment of the patient's disease (i.e., by physical examination).
5. Radiological assessment of disease status (i.e., chest X-ray, (chest CT or MRI only if indicated), pelvic/abdominal CT or MRI) must be performed  $\leq$  1 week prior to Cycle 4 and then at standard of care intervals. The methods used for prestudy assessments (e.g., CT or MRI) should be used throughout the study. If possible, the same equipment should be used each time.
6. A CBC with differential and platelet count.
7. CA-125 tumor assessment until recurrence. (monthly for the first year, then every 3 months  $\pm$  2 weeks for the second and third year.)
8. Serum chemistry and electrolytes.
9. Immune function analysis consisting of effector T cell response (ELISPOT assay will be monitored - Months 2, 4, 6 (prior to Vigil™ administration).
10. Assessment of PS on the ECOG scale (see Appendix A).
11. Vaccine administration. The patient will be observed for at least 30 minutes (with a 10% window) following vaccination. During this observation period, vital signs will be taken every 10 minutes (with a 10% window).
12. Day 2 assessment of injection site.
13. FACT-O, Version 4 assessment at baseline, Month 3, Month 6, Month 12 and Month 18 (or until recurrence).

Radiological assessment of disease status (i.e., chest X-ray, (chest CT or MRI only if indicated), pelvic/abdominal CT or MRI) must be collected if CA-125 >35 U/mL after two consecutive measurements taken one month apart.

### **Off Treatment Assessments**

The following evaluations will be performed within 30 days following the last Vigil™ administration and within 30 days of disease recurrence (unless otherwise specified):

1. A physical examination, including vital signs and body weight.
2. Toxicity assessment (adverse events) (Vigil™ administered patients only).
3. Assessment of concomitant medications taken.
4. Assessment of PS on the ECOG scale (see Appendix A).
5. A tumor clinical assessment of the patient's disease (i.e., by physical examination).
6. Radiological assessment of disease status (i.e., chest X-ray, (chest CT or MRI only if indicated), pelvic/abdominal CT or MRI) used to stage the extent of disease. (within 45 days of the last injection or disease recurrence)
7. A CBC with differential and platelet count.
8. CA-125 tumor assessment.
9. Serum chemistry and electrolytes.
10. Serum for immune function analysis consisting of ELISPOT analysis of cytotoxic T cell function to autologous tumor antigens.

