**Methodology:**

This is a Phase II open-label trial of Vigil™ autologous tumor cell vaccine. Tumor will be harvested at the time of surgical debulking (standard of medical care).

Patients achieving clinical complete response (CR) following primary surgical debulking and doublet chemotherapy will be stratified for i) surgical stage (Stage IV or suboptimal debulking (>1 cm residual) Stage III disease versus Stage III patients with optimal debulking (<1 cm residual)) and ii) post-operative chemotherapy, pre-vaccine CA-125 of greater than 10 but less than or equal to 20 U/mL versus 0≤10 U/ml then randomized 2:1 (Note: patients with Stage IIIC ovarian cancer will be additionally evaluated as a subset using descriptive statistical endpoint only). Patients will receive  $1.0 \times 10^7$  cells / intradermal injection of gene transfected autologous tumor cells, Vigil™, once a month for up to 12 doses as long as sufficient material is available. A minimum harvest aliquot to produce 4 monthly injections will be required for entry into the study. These patients will be managed in an outpatient setting. Hematologic function, liver enzymes, renal function and electrolytes will be monitored monthly. Immune function analysis including ELISPOT analysis of cytotoxic T cell function to autologous tumor antigens will be monitored at (≤24 hours before) tissue harvest, ≤24 hours before the first cycle chemotherapy (post debulking), ≤24 hours before the third cycle chemotherapy (post debulking), baseline (screening); prior to Vigil™ injection at Months 2, 4, 6 and EOT. CA-125 will be monitored at baseline, every month for the first year, every 3 months ± 2 weeks for the second and third year.

**Number of Patients:** Approximately fifty (50) patients with high risk Stage III/IV ovarian cancer.

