detectable autologous tumor specific cytotoxic CD8+ T-cell activity at baseline. Two patients showed ELISPOT reaction at baseline ( $\geq 10$  spots), but while one showed reactivity  $\geq 2$  times that of baseline at the Month 3 assessment, the other did not have a  $\geq 2$  times increase in ELISPOT spots, and thus was considered a negative responder. Twelve patients had an increase in immune response from a baseline mean of 6 IFN $\gamma$  producing T-cell spots to an end of Cycle 3 mean of 106 IFN $\gamma$  producing T-cell spots ( $p = 0.011$ ). The other 12 patient showed neither reactivity nor enhancement of immune response from a baseline mean of 3 spots through Cycle 3. These 2 populations were statistically different from each other at the end of Cycle 3 in ELISPOT response (106 spots vs. 3 spot,  $p=0.007$ ). Comparison of survival between the 12 patients demonstrating positive ELISPOT response and those 12 not demonstrating response at completion of Cycle 3 demonstrated a statistically significant increase in survival from time of procurement ( $p=0.040$ ) and time of treatment start ( $p=0.023$ , Figure 13a, b) in the former group. Additionally, patients who received  $\geq 3$  doses of Vigil™ and had a positive ELISPOT had better survival than patients who did not receive Vigil™ ( $p<0.001$ ).

[figure not shown]
**Figure 12.** IFN- $\gamma$  (ELISPOT) in FANG™ vaccine treated patients peripheral blood mononuclear cells in response to non-transfected autologous tumor cells. Blue lines indicate patients achieving  $\geq 10$  IFN- $\gamma$  producing lymphocytes (positive response) after 3 cycles of FANG™ vaccine. Red lines indicate patients not achieving positive ELISPOT response after 3 cycles of the FANG™ vaccine. (Data as of 01/08/13)

All patients demonstrating positive response after 3 complete cycles of Vigil™ vaccine who had long term assessment continued to show positive ELISPOT response during vaccine treatment and after discontinuation of vaccine therapy (Figure 12). Two patients who were in the non-responsive group at the end of Cycle 3 demonstrated a late positive response after 5 cycles of Vigil™ vaccine. One of these patients had advanced metastatic melanoma with survival of 490 days since treatment start, and the other had hepatocellular cancer with a survival of 738 days since treatment start.

a

b

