## 4.0 STUDY DESIGN

### 4.1 Design

This is a Phase II open-label trial of maintenance Vigil™ autologous tumor cell vaccine. Tumor will be harvested at the time of surgical debulking (standard of medical care). Subsequently, patients achieving clinical CR following primary surgical debulking and doublet chemotherapy will be stratified for i) surgical stage (Stage IV or suboptimal debulking (>1 cm residual) Stage III disease versus Stage III patients with optimal debulking (<1 cm residual)) and ii) post-op chemotherapy, pre-vaccine CA-125  $>10 \leq 20$  U/mL versus  $0 \leq 10$  U/ml, then randomized 2:1 (Note: patients with Stage IIIC ovarian cancer will be additionally evaluated as a subset using descriptive statistics only). Patients will receive  $1.0 \times 10^7$  cells / intradermal injection of gene transfected autologous tumor cells, Vigil™, once a month for up to 12 doses as long as sufficient material is available. Enough harvested tissue to provide a minimum of 4 monthly injections will be required for entry into the study. These patients will be managed in an outpatient setting. Hematologic function, liver enzymes, renal function and electrolytes will be monitored monthly. Immune function analysis including

ELISPOT analysis of cytotoxic T cell function to autologous tumor antigens will be monitored at ( $\leq$ 24 hours before) tissue harvest,  $\leq$ 24 hours before the first cycle of chemotherapy (post debulking),  $\leq$ 24 hours before the third cycle of chemotherapy (post debulking), baseline (screening), prior to Vigil™ injection Months 2, 4, 6 and at EOT. The dates of the last dose of chemotherapy and the administration of Vigil™ vaccine #1 will be recorded.

Treatment will be continued until disease recurrence or exhaustion of the patient's vaccine supply. If  $\geq$  Grade 2 toxicity by NCI Common Toxicity Criteria (excluding Grade 2 fever  $\leq$  24 hours and Grade 2 and 3 injection site reactions) develops related to study treatment the vaccine dose will be reduced by 50% and continued on a monthly basis. If a single patient develops  $\geq$  Grade 3 toxicity (other than injection site reaction) related to study treatment the trial will be placed on hold for reevaluation of design in discussion with FDA. During this hold, no new subjects will initiate dosing, but subjects already being dosed may continue dosing as scheduled if deemed clinically appropriate by the PI.

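### The off-treatment ELISPOT is specified on serum, which cannot be assayed for T cells, and it is the only scheduled late sample for patients whose vaccine runs out before Month 6

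*Combined protocol and SAP*

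**What the plan says.** **Specimen.** Item 10 of Off Treatment Assessments (Section 6.6) reads "Serum for immune function analysis consisting of ELISPOT analysis of cytotoxic T cell function to autologous tumor antigens". The list it belongs to is to be done "within 30 days following the last Vigil™ administration and within 30 days of disease recurrence". For the chemotherapy period, Prestudy Assessments in the same section says "Blood for immune function analysis will be collected prior to the first and third cycles of" chemotherapy. Section 1.10 describes the Phase I ELISPOT (Figure 12) as run on "peripheral blood mononuclear cells in response to non-transfected autologous tumor cells". The synopsis Methodology, Section 4.1 and Appendix B all schedule an end-of-treatment ELISPOT, and none of them names a specimen.

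**Timing.** Section 4.1 places the ELISPOT at "baseline (screening), prior to Vigil™ injection Months 2, 4, 6 and at EOT". Assessments During Treatment, item 9, has "ELISPOT assay will be monitored - Months 2, 4, 6 (prior to Vigil™ administration", and Appendix B ties the same months to vaccination. Section 6.4 allows 4 to 12 doses. Section 4.1 ends treatment at recurrence or when supply is used up. After that, Section 6.6 (Follow Up Assessments) provides quarterly telephone contact, with further blood or tissue optional and only at the sponsor's request. Appendix B shows no immune analysis in the follow-up column.

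**Use.** Effect on immune markers is a secondary objective (Section 3.2). Section 13.1 plans a descriptive report of the percentage and timing of ELISPOT conversion. The synopsis also lists the correlation of immune response with clinical effect as a trial endpoint.

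**The concern.** ELISPOT counts cells that secrete interferon gamma, so a cell-free specimen cannot give a result. A site working from item 10 could reasonably read it as a tube instruction. The item just before it is serum chemistry, and the follow-up text specifies whole blood by volume, so the protocol does distinguish specimens elsewhere.

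The wording matters because of the schedule around it. A patient whose supply ends early has no Month 6 injection and therefore no Month 6 draw. The off-treatment samples are then the only scheduled late measurement. If they are drawn as serum, late response and persistence after vaccine ends are unobserved in those patients.

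There is also a problem of interpretation. A Month 6 draw exists only in patients who still have vaccine and have not recurred. Being recurrence-free is part of the clinical outcome with which immune response is to be correlated.

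**Working it through.** The plan states no figure that depends on this point, so there is none to reproduce. The check compares the texts and then maps doses to sampling times.

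**1. Specimen, text against text**
- Chemotherapy time points (Section 6.6, Prestudy): blood.
- Phase I assay (Section 1.10, Figure 12): mononuclear cells.
- Baseline and Months 2, 4 and 6 (Section 6.6): no specimen named.
- End of treatment in the synopsis, Section 4.1 and Appendix B: no specimen named.
- Last dose and recurrence (Section 6.6, item 10): serum.

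Item 10 is the only line that names serum for this assay, and no other line on that visit corrects it.

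**2. Which patients have a Month 6 draw**

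Inputs: dosing every 28 days (Section 6.6), 4 to 12 doses (Section 6.4), and an off-treatment visit within 30 days of the last dose (Section 6.6). Take the first dose as day 0. The last of D doses falls on day 28 × (D − 1), and the off-treatment window closes 30 days later.

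The month count can be read in two ways:
- Reading A: Month k is before dose k. Month 6 is then day 28 × 5 = 140.
- Reading B: Month k is before dose k + 1. Month 6 is then day 28 × 6 = 168. Section 1.10 supports this reading, because the Phase I draw before the fourth dose is also called the Month 3 assessment.

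| Doses | Last dose, day | Window closes, day | ELISPOT months, A | ELISPOT months, B |
|---|---|---|---|---|
| 4 | 84 | 114 | 2, 4 | 2 |
| 5 | 112 | 142 | 2, 4 | 2, 4 |
| 6 | 140 | 170 | 2, 4, 6 | 2, 4 |
| 7 | 168 | 198 | 2, 4, 6 | 2, 4, 6 |

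Month 6 needs six doses under A and seven under B. Under B a four-dose patient also misses Month 4. A four-dose patient's window closes 140 − 114 = 26 days (A) or 168 − 114 = 54 days (B) before nominal Month 6. With five doses under A, or six under B, the window closes 2 days after nominal Month 6.

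**3. Recurrence before Month 6 (illustration)**

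Assume exponential times with the control medians in Section 13.1, so the share recurring by t months is 1 − 2^(−t/median). Months 5 and 6 round up from days 140 and 168, so the results are slightly high.
- Median 24 months: 13% at 5 months, 16% at 6.
- Median 16 months: 19% at 5 months, 23% at 6.

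**4. Effect on the reported conversion rate (illustration)**

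The dose distribution is not given. If 10% to 50% of 50 patients lack Month 6 (assumed), 45 to 25 remain. The exact 95% interval around roughly 50% conversion is then 34% to 64% (22 of 45) or 28% to 69% (12 of 25).

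For selection, let true conversion be 50%, the missing share f, and conversion among the missing p. The observed rate is (0.50 − f × p)/(1 − f). With f = 0.30:
- p = 0.25 gives 0.425/0.70 = 61%.
- p = 0.40 gives 0.38/0.70 = 54%.
- p = 0.60 gives 0.32/0.70 = 46%.

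The direction depends on p, which the documents do not give.

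**The case against.** The strongest reply is that this is one wrong word. Item 10 names its own assay, a T-cell ELISPOT, and a laboratory that knows the assay would ask for cells. The end-of-treatment ELISPOT is scheduled in three other places without mention of serum. That stands as far as consequence goes: the loss occurs only if sites follow the line literally. It does not remove the conflict, because the line is a current operative instruction.

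The second reply is that patients without a Month 6 draw are not left unmeasured. The off-treatment list applies after the last dose and again at recurrence, and extra whole blood can be requested. This also stands. Once the specimen is corrected, what remains is late sampling whose day varies with dose count, plus the condition of being recurrence-free at Month 6.

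A reader might draw four stronger conclusions that the documents do not support:
- *That the end-of-treatment ELISPOT data are lost.* They are at risk under a literal reading; loss is not shown.
- *That Phase I measures the loss.* There, 2 of 12 early non-responders turned positive after five cycles, which moves response from 12/24 (50%) to 14/24 (58%). A four-dose patient never reaches five cycles, and a five-dose patient has an off-treatment sample within 30 days of dose five. The figures show only that late conversion happens.
- *That the Month 6 group is favourably selected overall.* Selection on being recurrence-free is real. Selection through vaccine supply could go either way: Section 6.2 links doses to the tissue collected, and Section 13.1 hypothesises that larger tumor volume goes with weaker immune response.
- *That a particular number of patients is affected.* Any count rests on an assumed dose distribution and on which month reading applies.

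**Conclusion.** Item 10 is wrong as written and should be corrected. It puts the last-dose and recurrence ELISPOT samples at risk in every patient. For patients whose vaccine runs out before Month 6, those are the only scheduled late samples.

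The Month 6 issue is real but smaller. The draw needs six or seven doses depending on an undefined month count, and four suffice for entry. With the specimen corrected, the residual problem is variable timing, with a shortfall of 26 to 54 days for a four-dose patient, and selection on being recurrence-free.

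The timing figures assume 28-day dosing without delay. The recurrence, precision and selection figures are illustrations under stated assumptions. The immune endpoint is secondary and descriptive, the Phase I benchmark in Section 13.1 is conversion by Month 4, and the primary time-to-recurrence analysis is unaffected.

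**What to change.** 1. Change item 10 to whole blood for mononuclear cells, and name that specimen at every ELISPOT time point in Section 6.6 and Appendix B. This costs a short wording correction.
2. State whether Month k means before dose k or before dose k + 1. This costs one sentence.
3. Report conversion at each time point with the number sampled and the number of dosed patients, by dose count. Do not silently count an unsampled patient as a non-converter. Where there is no Month 6 injection, use the end-of-treatment sample as the late assessment and record its actual day. This needs reporting text only.
4. Optionally, add a calendar Month 6 draw alongside the first-year monthly CA-125. The cost is small but not nil: follow-up after vaccine ends is otherwise by telephone, so a visit and cell handling may have to be arranged. The draw would also mix patients on and off vaccine, so results should be shown separately by that status.

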### **Follow Up Assessments**

If the Vigil™ vaccine is discontinued (for reasons such as completion of all available doses of vaccine, intolerable toxicity, treatment interruption of more than 4 weeks, intercurrent illness, protocol deviation at PI's discretion), the patient will be contacted by phone every 3 months after the end of study visit for:

- disease status
- request of medical records, when applicable (laboratory findings, radiological scans, and progress report)
- documentation of 2nd line therapy
- recording of response and duration of response to that therapy
- survival
- assessment of any additional cancer treatments)

**Note:** Patients who die or withdraw consent are considered **off study** and no further information except survival data will be collected.

Based on findings during the study or during the follow up portion of the trial, Gradalis may request for additional blood and / or tissue samples from the research participant. Collection of whole blood (40ml) and / or tissue samples (via biopsy or clinically indicated surgical removal) will be **optional** and used to study the effects of the study agent (included, but not limited to testing of biomarkers, predictors or biological responses, toxicity, relationship between genotype and study agent responses).

Should Gradalis request for additional blood or tissue, the clinical site will present the option of the procurement to the participant and obtain written informed consent.

